##### **AEs Secondary to other Events**

During case processing, in general, AEs secondary to other events (e.g. cascade events or clinical sequelae) should be recorded based on their main etiology, except for severe or serious secondary AEs. For a medically significant AE secondary to an initial event with a time interval, the AE should be recorded as an independent event.

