### 1.2.3 Post-authorisation Experience

The cumulative exposure to Compound Sodium Picosulfate Granules from marketing experience calculated from 01 January 1999 up to and including 31 May 2019 is estimated to 53,654,394 patients. The calculation of exposure is based upon an assumption that the number of treatments is equivalent with number of patients exposed to Compound Sodium Picosulfate Granules. One treatment consists of 2 sachets, which corresponds to an adult dose.

The frequencies of the side effects are based on post-marketing experience and as outlined in the Compound Sodium Picosulfate Granules label.

System Organ Class	Common ( $\geq 1/100$ , $< 1/10$ )	Uncommon ( $\geq 1/1000$ , $< 1/100$ )	Not known (cannot be estimated from the available data)
Immune system disorder		Anaphylactic reaction, hypersensitivity	
Metabolism and nutrition disorders		Hyponatraemia hypokalaemia	
Nervous system disorders	Headache	Epilepsy, grand mal convulsion, convulsions, confusional state	
Gastrointestinal disorders	Nausea and proctalgia	Vomiting, abdominal pain, aphthoid ileal ulcers	Diarrhoea, faecal incontinence
Skin and subcutaneous tissue disorders		Rash (including erythematous and maculopapular rash, urticaria, purpura)	

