### 1.3 Study Rationale

Based on nearly 40 years' clinical experience, Compound Sodium Picosulfate Granules has a well-

established safety profile and treatment regimen that support a positive benefit/risk ratio.

According to the review of non-clinical, clinical and post-marketing data, the known adverse effects of Compound Sodium Picosulfate Granules include anaphylactic reaction, hypersensitivity, hyponatraemia, hypokalaemia, confusional state including disorientation, headache, epilepsy, generalised tonic-clonic seizure, seizure, loss of consciousness or depressed level of consciousness, syncope, presyncope, dizziness, vomiting, nausea, abdominal pain, diarrhoea, ileal ulcers, anal incontinence, proctalgia, rash (including erythematous rash, maculo-papular rash, urticaria, purpura).

According to the latest Compound Sodium Picosulfate Granules Risk Management Plan (RMP) (Ver. 2.0, 11 OCT 2019), Compound Sodium Picosulfate Granules has no important identified risks, no important potential risks, and no important missing information. Compound Sodium Picosulfate Granules's label and its package leaflet give essential information to healthcare professionals and patients on how the Compound Sodium Picosulfate Granules product should be used. Measures to minimise the risks identified for medicinal products include:

- Specific information, such as warnings, precautions, and advice on correct use, in the package leaflet and label addressed to patients and healthcare professionals;
- Important advice on the medicine's packaging;
- The authorised pack size — the amount of medicine in a pack is chosen so to ensure that the medicine is used correctly;
- The medicine's legal status — the way a medicine is supplied to the patient (e.g. with prescription) can help to minimise its risks.

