## 2 STUDY OBJECTIVES

The objectives of this drug intensive monitoring study are to monitor and assess the safety profile of Compound Sodium Picosulfate Granules in the real world clinical practice in Chinese population, including:

- Incidence of known ADRs
- Observe occurrence of unexpected AEs/ADRs
- Incidence and risk factors of SAEs/SADRs

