#### **6.7.6      *Special Situations with No Need to Record as AEs***

During case processing, the following situations collected will not be recorded as AEs:

- The clinical adverse events that occurred before the medication will be recorded as pre-treatment events rather than AEs.
- Since abdominal bloating, distension and watery diarrhoea are known to occur in response to bowel preparations, these effects should be documented as AEs only if they require medical intervention (such as a change in study drug or led to study discontinuation, therapeutic or diagnostic procedures), or show clinically significant worsening during the study that is not in the frame of the usual clinical course.
- X-ray examination, endoscopy or bowel surgery findings such as polyps and/or colorectal cancer do not need to be recorded as an AE as their diagnosis is the goal of the endoscopic examination. However, injuries / damages caused by inspections or surgical operations must be recorded as AEs.

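### Sections 6.7.5 and 6.7.6 together let a mild reaction attributed to ordinary diarrhoea, bloating or distension go uncounted, so the incidence of known ADRs can be understated by an unknown amount

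*Combined protocol and SAP*

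**What the plan says.** The rules come from the case-processing part of the protocol.

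- **Section 6.7.5, secondary events.** As a general rule, "AEs secondary to other events (e.g. cascade events or clinical sequelae) should be recorded based on their main etiology". Events are outside the rule under "except for severe or serious secondary AEs". There is one further carve-out: "For a medically significant AE secondary to an initial event with a time interval, the AE should be recorded as an independent event".
- **Section 6.7.6, effects not recorded.** The section explains that "abdominal bloating, distension and watery diarrhoea are known to occur in response to bowel preparations" and that "these effects should be documented as AEs only if they require medical intervention", or if they worsen in a clinically significant way beyond the usual course.
- **Section 6.7.1, description of events.** Every separate diagnosis, sign or symptom counts as an AE.
- **Section 6.7, variables per AE.** Seriousness and its criteria are listed. A severity or intensity grade is not.
- **Section 2, objectives.** The first item is "Incidence of known ADRs". Section 7.3.3 makes the incidence of known and unexpected ADRs/AEs the main content of the safety tables.
- **Section 1.3, known effects.** The list includes "syncope, presyncope, dizziness, vomiting, nausea, abdominal pain, diarrhoea, ileal ulcers, anal incontinence, proctalgia". In the table in Section 1.2.3, "Nausea and proctalgia" are the gastrointestinal entries in the common band (at least 1/100, below 1/10).

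**The concern.** Each rule is understandable alone. Recording the primary event rather than every consequence avoids double counting, and not recording the intended effect of a purgative avoids swamping the tables. The difficulty is the combination. The first rule moves a mild event to its cause, and the second leaves that cause out of the AE record. No sentence covers an event whose cause has been left out.

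The product works by purging the bowel (Section 1.1), so ordinary diarrhoea is a cause readily at hand for a mild complaint in the same hours. Whether the complaint is counted then depends on how one case processor reads the causal chain. The resulting error goes one way, towards a lower recorded incidence of known reactions. No table planned in Sections 7.3.2 or 7.3.3 shows events that were folded into another event or exempted, so a reader of the report could not see it.

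**Working it through.** The plan states no figure on this point. There is no sample size target, test or expected event count to reproduce. The check is therefore a reading of the rules in sequence, followed by arithmetic for scale.

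**Step 1. One case under the rules.** Take a subject with mild proctalgia that the case processor attributes to ordinary watery diarrhoea.

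| Rule | Result |
|---|---|
| 6.7.1, each symptom is an AE | Points to recording proctalgia |
| 6.7.5, default for secondary events | Record under the main cause, diarrhoea |
| 6.7.5, severe or serious exception | Not met |
| 6.7.5, medically significant with a time interval | Not met |
| 6.7.6, diarrhoea needing intervention or worsening beyond the usual course | Not met, so diarrhoea is not recorded |
| Net result if 6.7.5 is followed | Neither event is in the AE record |

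Section 6.7.1 does not settle this. It is the general rule and 6.7.5 is the specific one, and the text does not say which prevails. Two processors could each follow the protocol and record the same subject differently.

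**Step 2. Which known reactions are exposed.**

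- Proctalgia, anal incontinence and mild dizziness are the plausible set. They are on the Section 1.3 list, they are not on the 6.7.6 list, and in mild form they would usually meet no exception.
- Hyponatraemia and hypokalaemia are much less exposed. The part of 6.7.5 on abnormal examinations records an abnormality that comes with symptoms or needs intervention, and uses low sodium as an example.
- Syncope may meet the severe, serious or medically significant exceptions. Presyncope may too.

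**Step 3. The severe exception.** It needs a severity judgement. The variable list in 6.7 has none, and the AE items named in Section 5 include seriousness but not severity. The exception therefore cannot be applied, or checked later, from a recorded variable.

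**Step 4. Scale.** Let p be the true incidence and f the share of cases judged secondary to an unrecorded effect and outside every exception.

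Recorded incidence = p × (1 − f)

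Recorded incidence falls below 1/100 when f > 1 − 0.01/p.

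The documents give the band for p but no value of f, so f is an assumption varied over its whole range.

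| True p | f = 25% | f = 50% | f = 75% | f = 100% | Falls below 1/100 when |
|---|---|---|---|---|---|
| 1% | 0.75% | 0.50% | 0.25% | 0% | f > 0 |
| 2% | 1.50% | 1.00% | 0.50% | 0% | f > 1 − 0.01/0.02 = 50% |
| 3% | 2.25% | 1.50% | 0.75% | 0% | f > 1 − 0.01/0.03 = 66.7% |
| 5% | 3.75% | 2.50% | 1.25% | 0% | f > 1 − 0.01/0.05 = 80% |

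Of the three reactions in Step 2, only proctalgia has a numerical band in Section 1.2.3. Faecal incontinence is listed there with unknown frequency, and dizziness is not in that table.

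**The case against.** The best defence is that the text never tells anyone to discard an event. The cascade rule is stated only as a general one. Proctalgia, incontinence and dizziness are not among the things 6.7.6 excludes, and 6.7.1 lets a processor record the symptom when no recordable cause exists. Sites send all collected AEs to the sponsor (Section 6.5), so nothing is lost before case processing. The study is descriptive, with no tests and no planned comparison against label frequency bands. Section 1.2.2 also reports a similar exemption in the earlier clinical trials, and that one covered pain and cramping too.

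Much of this stands as a limit on size. It does not close the gap, because a processor who follows 6.7.5 literally is also compliant, and the two readings give different counts.

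A reader might infer more than the documents support:

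- **That known reactions disappear from the tables altogether.** For any one reaction this needs f = 100%. The supported conclusion is that individual cases may be missing.
- **That diarrhoea is the commonest cause of secondary events.** The documents say only that these effects are known to occur. They attribute none of the listed reactions to diarrhoea.
- **That about a third of the Section 1.3 list is exposed (7 of 21 terms, adding syncope, presyncope, hyponatraemia and hypokalaemia).** The routes in Step 2 cover much of that addition.
- **That mild dizziness folded into vomiting is the same fault.** There the vomiting is itself a countable event, and the folding is an openly stated convention.

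**Conclusion.** The point holds as a gap in the recording rules. A secondary event that is not severe, not serious, and not both medically significant and separated in time can be assigned to ordinary watery diarrhoea, bloating or distension. These are not recorded, so cases of known reactions can be under-counted in the study's first listed objective. The conflict between 6.7.5 and 6.7.1, and a severity exception with no severity variable, make the count depend on the processor.

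The size cannot be stated, because it rests on f, for which the documents give no value. A modest f leaves a reaction well inside the common band in its band. Moving one out takes f above 50% at a true 2% and above 80% at a true 5%. Which mild events would be attributed to diarrhoea is a case-level clinical judgement, and naming proctalgia, anal incontinence and dizziness is an inference from the lists in Sections 1.3 and 6.7.6. The point is moderate: the direction of the error is clear, its size is unknown, and the cases are recoverable because the sponsor receives the reports.

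**What to change.** Make three changes.

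1. Add to Section 6.7.5: *An event judged secondary to an effect that is not recorded as an AE under Section 6.7.6 is recorded as an AE in its own right, with the presumed cause noted.*
2. State how the cascade rule in 6.7.5 relates to the one-symptom rule in 6.7.1, so that the same case is processed the same way each time.
3. Either define severity and add it to the variables in Section 6.7, or drop it as an exception in 6.7.5.

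Leave the 6.7.6 exemption for ordinary diarrhoea, bloating and distension as it is. A wider rule that always records any term in Section 1.3 should be avoided: diarrhoea is on that list, so the rule would contradict 6.7.6.

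The cost is a short text change, a matching line in the case-processing instructions, and somewhat more non-serious AE records to process. Cases already processed can be checked against the reports that sites sent to the sponsor.

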##### **Abnormal Medical Exam**

Clinically significant medical exam abnormalities (such as vital signs, physical examination, blood routine, urine routine, blood biochemistry, ECG, etc.) found before the first medication can be recorded as a medical history/concomitant disease. The results of various medical exam after medication will be compared with the data from baseline and judged whether they are of clinical significance.

During case processing, medical exam abnormalities should be recorded as an AE if any one of

the following criteria is met:

- The abnormality is associated with symptoms/signs.
- The abnormality requires required medical intervention (such as a change in medicinal product or led to study discontinuation, therapeutic or diagnostic procedures).

If the abnormality is a manifestation of a disease (e.g. increased alkaline phosphatase and total bilirubin levels accompanied by cholecystitis), only the diagnosis (i.e. cholecystitis) should be recorded as an AE. If the abnormality does not belong to any disease, the abnormality itself should be recorded as an AE, using relevant descriptors to indicate that the test result is higher or lower than the normal range (e.g. “blood sodium decreased” instead of “blood sodium abnormal”). If the diagnostic criteria are met, the clinical diagnosis should be used to record the AE. For example, a serum sodium level < 135 mmol/L can be recorded as “hyponatremia”.

#### **6.7.6      *Special Situations with No Need to Record as AEs***

During case processing, the following situations collected will not be recorded as AEs:

- The clinical adverse events that occurred before the medication will be recorded as pre-treatment events rather than AEs.
- Since abdominal bloating, distension and watery diarrhoea are known to occur in response to bowel preparations, these effects should be documented as AEs only if they require medical intervention (such as a change in study drug or led to study discontinuation, therapeutic or diagnostic procedures), or show clinically significant worsening during the study that is not in the frame of the usual clinical course.
- X-ray examination, endoscopy or bowel surgery findings such as polyps and/or colorectal cancer do not need to be recorded as an AE as their diagnosis is the goal of the endoscopic examination. However, injuries / damages caused by inspections or surgical operations must be recorded as AEs.

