In randomized, multicentre, controlled clinical trials, nausea, headache, and vomiting were the most common adverse reactions (>1%) following Compound Sodium Picosulfate Granules administration. Since abdominal bloating, distension, pain/cramping, and watery diarrhoea are known

to occur in response to bowel cleansing preparations, these effects were documented as adverse events in the clinical trials only if they required medical intervention (such as a change in study drug or led to study discontinuation, therapeutic or diagnostic procedures, met the criteria for a serious adverse event), or showed clinically significant worsening during the study that was not in the frame of the usual clinical course, as determined by the investigator.

Limitations in respect to populations typically under-represented in clinical trial development programmes are presented as follows:

Paediatric population	In completed Ferring sponsored clinical trial for the paediatric population (000103), a total of 78 paediatric subjects were included (48 paediatric subjects were randomised to Compound Sodium Picosulfate Granules and 30 to PEG). The subjects were randomised to one of the treatment arms by age groups from 9-12 years and 13-16 years. The Compound Sodium Picosulfate Granules age group 9-12 years received either 1/2 sachet x 2 or 1 sachet x 2, whilst the Compound Sodium Picosulfate Granules age group 13-16 years received 1 sachet x 2. The results of the trial demonstrated that the '1 sachet x 2 dose' of Compound Sodium Picosulfate Granules is a safe and efficacious preparation for colonoscopy in children aged 9-16 years.
Elderly	In the completed Ferring sponsored clinical trials 20% of patients were of $\geq$ 65 years of age. The overall incidence of treatment emergent adverse events was similar among patients of $\geq$ 65 and $<$ 65 years of age, 73% and 71% respectively.

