#### 6.4 Definition of Serious Adverse Events

A serious adverse event (SAE) is defined as any untoward medical occurrence that at any dose that:

- Results in death a
- Is life-threatening b
- Is a congenital anomaly/birth defect c
- Results in persistent or significant disability/incapacity d
- Results in unplanned inpatient hospitalisation or prolongation of existing hospitalisation e
- Is an important medical event that may jeopardise the subject or may require intervention to prevent one of the outcomes listed above f

Further explanations for SAEs are as follows:

- a. Any deaths caused by AEs during the study period, including those that are completely unrelated to the medicinal product. Note: AE terms should be described as the lead cause of death (e.g. multiple organ dysfunction syndrome, pneumonia, myocardial infarction, etc. and with a fatal outcome but not death as an event), with the only exception being unknown causes of death (i.e. sudden or unexplained death), in which case the event term may be "death" or "sudden death".
- b. Life-threatening is an event that places the patient at immediate risk of death from the reaction as it occurred. It does not include a reaction that, had it occurred in a more severe form, might have caused death, e.g. drug-induced liver injury without hepatic failure.
- c. The term refers to any congenital anomaly/birth defect in the offspring of either patient who exposed to the medicinal product.
- d. The term refers to any condition that impairs physical/psychological well-being to the extent that the subject is unable to function normally. Physical disability may include, but is not limited to, permanent disability of locomotion or motility, but also systemic permanent dysfunction as development of heart failure, liver insufficiency or pulmonary fibrosis.

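### The recording threshold for bloating, distension and watery diarrhoea does not name seriousness, which leaves a narrow gap against the SAE definition, and the diarrhoea incidence it yields needs a footnote

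*Combined protocol and SAP*

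**What the plan says.** Section 6.7.6 lists situations that will not be recorded as AEs during case processing. For abdominal bloating, distension and watery diarrhoea it states that "these effects should be documented as AEs only if they require medical intervention", and continues with examples and a second trigger: "such as a change in study drug or led to study discontinuation, therapeutic or diagnostic procedures), or show clinically significant worsening during the study", the worsening being outside the usual clinical course.

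Section 1.2.2 describes the rule used in the sponsor's clinical trials. It opens "Since abdominal bloating, distension, pain/cramping, and watery diarrhoea are known" to follow bowel cleansing, and its examples of intervention run on to include "therapeutic or diagnostic procedures, met the criteria for a serious adverse event".

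Section 6.4 defines as serious any event that "Results in unplanned inpatient hospitalisation or prolongation of existing hospitalisation". Its note e accepts, as one reason for admission, specific monitoring of a subject whose condition is unstable.

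Section 2 names "Incidence of known ADRs" and the incidence of SAEs among the objectives. The synopsis says that the incidence of each AE will be calculated, and Section 7.3.3 plans a descriptive summary of SAEs. Section 1.3 lists diarrhoea among the known adverse effects. The table in Section 1.2.3 places "Diarrhoea, faecal incontinence" in the column for effects whose frequency is not known.

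**The concern.** Two separate issues arise from the same rule.

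The first concerns SAEs. The rule works by exclusion: an effect that meets neither trigger is not an AE in this study, so it cannot appear as an SAE. If seriousness is not itself a reason to record, an event can meet the definition in Section 6.4 and still be filtered out before the SAE tables are built. In a safety monitoring study, the recording rule and the seriousness definition should not be able to disagree.

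The second concerns the meaning of the diarrhoea figure. Its frequency is one that the label could not estimate, so readers are likely to look for it in the report. What they will find is the incidence of diarrhoea that passed a threshold. Neither the limitations in Section 3.3 nor the analysis text in Section 7.3 says this.

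**Working it through.** The documents give no SAE rate, diarrhoea rate or sample size to reproduce, so the check is a comparison of texts plus one identity.

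**Step 1. The two rules side by side.**

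| Element | Section 1.2.2 (sponsor's trials) | Section 6.7.6 (this study) |
|---|---|---|
| Effects covered | Bloating, distension, pain/cramping, watery diarrhoea | Bloating, distension, watery diarrhoea |
| Trigger 1 | Medical intervention; open list of examples that includes meeting SAE criteria | Medical intervention; open list of examples without the SAE item |
| Trigger 2 | Significant worsening beyond the usual course, judged by the investigator | The same, with no judge named |

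Both rules have two triggers. In Section 1.2.2 seriousness is an example within the first trigger, not a third trigger. The study rule loses that example. It also covers one effect fewer, so abdominal pain is unfiltered here while diarrhoea is filtered.

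**Step 2. Does another section restore a seriousness override?** Section 6.7.5 has two candidates. The paragraph on persistent events requires an update when an event becomes serious, but this applies to an event already recorded. The paragraph on secondary events exempts severe or serious ones, but only those secondary to another event. Neither reaches a primary report of diarrhoea, bloating or distension.

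**Step 3. A test case.** Take a subject kept in hospital overnight because of watery diarrhoea.

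- If the stay is for tests or treatment, those are diagnostic or therapeutic procedures. Trigger 1 is met and the event is recorded.
- If the stay is for monitoring alone, it can still be serious under Section 6.4 and note e. Trigger 1 is not plainly met. Recording then depends on someone judging that the diarrhoea worsened beyond the usual course.
- If that judgement is not made, the event is serious under Section 6.4 and unrecorded under Section 6.7.6.

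Only the last branch is a gap.

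**Step 4. What the diarrhoea row measures.** Let p be the share of subjects with any watery diarrhoea and q the share of those who meet a trigger. The reported incidence is p × q. The documents give neither quantity. With q assumed to lie anywhere from 0 to 1, the reported value lies anywhere from 0 to p. Adding a seriousness clause can only raise q or leave it unchanged; it does not make q equal to 1. The second issue therefore comes from the threshold itself, which the trial rule shared, and needs its own remedy.

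**The case against.** The strongest reply is that little is lost. An example dropped from an open list is weaker than a removed trigger, and a sensible case processor would still treat an SAE as recordable. Note e in Section 6.4 excludes stays for convenience and ties monitoring to an unstable condition, which would ordinarily count as significant worsening. This stands, and it is why the gap is narrow. It does not close the gap, because the rule is worded as an exclusion and leaves the outcome to a judgement that the seriousness definition does not require.

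The threshold itself is also defensible. The product is given for its purgative effect (Section 1.1), and Sections 6.1 and 6.2 define AEs and ADRs in terms of unintended effects. Ordinary watery diarrhoea after a bowel cleanser need not be an AE. This stands too: the point is disclosure, not the existence of a threshold.

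A reader might infer four stronger things that the documents do not support.

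- *That the incidence of diarrhoea cannot be reported.* It can be, for events above the threshold; only the overall incidence is unavailable.
- *That leaving out the investigator is a defect.* The synopsis gives signatory investigators as not applicable, and Section 6.7 makes the sponsor responsible for case processing, so the omission fits the design.
- *That filtered reports are destroyed.* Section 6.5 says the sponsor captures AEs collected at the contact, and Section 6.7.6 says only that these situations are not recorded as AEs.
- *That the loss of SAEs can be expressed as a percentage.* Section 7.1 sets no sample size, the version history shows that the planned 3,000 was deleted, and no SAE rate is given.

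**Conclusion.** The point holds in a limited form. Section 6.7.6 omits the seriousness example that the sponsor's trial rule carried, and nothing else supplies it for these three effects. On a literal reading, a monitoring-only admission could be serious under Section 6.4 yet absent from the SAE summary. Few events are likely to be affected, since most serious ones would meet an existing trigger, but the number cannot be estimated from the documents. The conclusion rests on reading the exclusion as written and on such a stay not being counted as an intervention or as unusual worsening.

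The diarrhoea, bloating and distension rows will show incidence above a recording threshold, not overall incidence. That is acceptable if stated. Both matters bear on stated objectives and should be corrected, though neither undermines the study.

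**What to change.** 1. Reconcile Section 6.7.6 with Sections 1.2.2 and 6.4 by adding to the triggers: *or meet any seriousness criterion in Section 6.4*.
2. In Section 7.3.3 and the table shells, footnote the diarrhoea, bloating and distension rows as counting only events that required medical intervention, were serious, or worsened significantly beyond the usual course, and say that they are not overall incidences.
3. Optionally, show the reports of these effects that fell below the threshold in a separate row per term. Label the row as reports received, because the documents do not show that subjects are asked about these effects systematically.

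Items 1 and 2 cost one clause and one footnote, with no new contact, test or data field. Item 3 would need a simple tally of reports that reach the sponsor before the filter is applied.
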